8.7 Columbia Suicide Severity Scale (C-SSRS)

Suicidality will be monitored during the trial (excluding the 21-day follow-up period) using the C-SSRS (Child Version). Suicidality data will be collected at all the visits including the scheduled visits and the ET visit.

Variables pertaining to suicidality assessments are categorical in nature. For each of the suicidality categories of interest, the number and percentage of subjects with the presence of suicidality will be tabulated (or say, summarized) by visit and for the overall treatment period. Note that, the presence of suicidality is defined as reporting of at least one occurrence of any types of suicidal ideation or behavior. Also note that, for the tabulation for the overall treatment period, a subject will be counted only once if he or she had multiple occurrences of suicidal ideation or behavior during the treatment period.

And the following four categories of treatment emergent suicidality will be analogously summarized: (1) Emergence of suicidal ideation, which is defined as reporting of any types of suicidal ideation during the treatment period while there was no suicidal ideation at baseline; (2) Emergence of serious suicidal ideation, which is defined as having observation of suicidal ideation severity rating of 4 or 5 during the treatment period while there was no suicidal ideation at baseline; (3) Worsening of suicidal ideation, which is defined as having a suicidal ideation severity rating that is more severe compared to baseline; (4) Emergence of suicidal behavior, which is defined as reporting of any types of suicidal behavior during the treatment period while there was no suicidal behavior at baseline. Specifically, for each of the above categories of treatment emergent suicidality, descriptive statistics in the form of count and percentage of the subjects who experienced such an event will be calculated on the OC data by visit and for the overall treatment period.

There are 4 specific types of suicidal behavior and 5 specific types of suicidal ideation. The number and percentage of subjects who experienced any of those types of behavior or ideation will be tabulated on the OC data by visit and for the overall treatment period.

Wherever applicable, assessments on all individual questionnaires pertaining to suicidal behavior or ideation will be summarized by visit by using the descriptive statistics for categorical variables.

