7.4 Medical and Psychiatric History

Medical history and psychiatric history data will be summarized on the Enrolled Sample by prior treatment group using descriptive statistics.

8 Safety Analysis

All safety analyses specified in this section will be performed on the Safety Sample. The baseline of a safety variable is defined as the last observation or assessment in the variable prior to the first dose of the open-label IMP.

Safety is the primary objective for this study. Safety will be assessed by the following standard endpoints for clinical trials and trials of antipsychotic drugs:

- The frequency and severity of treatment-emergent adverse events (TEAEs), serious TEAEs, and discontinuation from trial due to AEs.
- Change from baseline to post-baseline time points in: a) vital sign measurements; b) electrocardiogram (ECG) parameters; c) clinical laboratory tests (including prolactin) and urinalysis; and d) physical examination findings.

- Analysis of potential suicide events recorded on the Columbia-Suicide Severity Rating Scale (C-SSRS).
- Changes from baseline to post-baseline time points in results from extrapyramidal symptoms (EPS) scales (Simpson Angus Scale [SAS], Abnormal Involuntary Movement Scale [AIMS], and Barnes Akathisia Rating Scale [BARS]).
- Percentage of subjects with clinically significant changes in weight (gain or loss) from baseline to specified time points.
- Time to discontinuation.

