11.8 Columbia-Suicide Severity Rating Scale (C-SSRS)

Suicidality will be monitored at all visits during the trial (excluding the 21-day follow-up period) using the C-SSRS (Child Version). The "Since Last Visit" of the scale will be completed for all subjects at all visits. For subjects in this trial, the pediatric version will be used and may be completed with caregiver assistance if required.

Suicidal ideation has 5 types of ideations with increasing severity from Type 1 to Type 5. A subject can report or can be rated with multiple types of ideations at the visit level. The most severe type of ideation on the subject at the visit level will be used for data summary purpose. The variable Intensity of Suicidal Ideation also has 4 other dimensions, which are the frequency of ideation, duration of ideation, controllability, and deterrents, each of which is rated on a scale of 0 to 5 or 1 to 5, with higher integers representing more worse clinical outcomes.

12 Proposed List of Summary Tables

- CT-1.1.1 Subject Disposition (Enrolled Sample)
- CT-1.1.2 Subject Disposition by Clinical Trial Center (Enrolled Sample)
- CT-1.1.3.1 Subject Disposition by Gender (Enrolled Sample)
- CT-1.1.3.2 Subject Disposition by Race (Enrolled Sample)
- CT-1.1.3.3 Subject Disposition by Age Group (Enrolled Sample)
- CT-1.1.3.4 Subject Disposition by Body Weight Group (Enrolled Sample)
- CT-1.2 Subject Completion Rate by Week (Enrolled Sample)
- CT-2.1.1 Reasons for Discontinuation (Enrolled Sample)
- CT-2.1.2 Reasons for Discontinuation Due to COVID-19 (Enrolled Sample)
- CT-2.1.3.1 Reasons for Discontinuation by Gender (Enrolled Sample)
- CT-2.1.3.2 Reasons for Discontinuation by Race (Enrolled Sample)
- CT-2.1.3.3 Reasons for Discontinuation by Age Group (Enrolled Sample)
- CT-2.1.3.4 Reasons for Discontinuation by Body Weight Group (Enrolled Sample)
- CT-3.1.1 Demographic Characteristics (Enrolled Sample)
- CT-3.1.2.1 Demographic Characteristics by Gender (Enrolled Sample)
- CT-3.1.2.2 Demographic Characteristics by Race (Enrolled Sample)
- CT-3.1.2.3 Demographic Characteristics by Age Group (Enrolled Sample)
- CT-3.1.2.4 Demographic Characteristics by Body Weight Group (Enrolled Sample)
- CT-3.2 Medical History (Enrolled Sample)
- CT-3.3 Psychiatric History (Enrolled Sample)
- CT-3.4.1 Baseline Psychiatric Scale Evaluation (Enrolled Sample)
- CT-3.4.2.1 Baseline Psychiatric Scale Evaluation by Gender (Enrolled Sample)

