- CT-12.2.1 Listing of Potentially Clinically Relevant Abnormalities in ECG Evaluations (Safety Sample)
- CT-12.2.2 Incidence of Potentially Clinically Relevant Changes in ECG Evaluations (Safety Sample)
- CT-12.2.3 Summary of Change from Baseline in Electrocardiogram Results by Visit (Safety Sample)
- CT-12.3.1 Listing of Categorical Changes in QT/QTc (Safety Sample)
- CT-12.3.2 Incidence of Categorical Changes in QT/QTc (Safety Sample)
- CT-13.1.1 Columbia-Suicide Severity Rating Scale(C-SSRS), Suicidality (Safety Sample)
- CT-13.1.2 Columbia-Suicide Severity Rating Scale(C-SSRS), Suicidal Ideation by Type (Safety Sample)
- CT-13.1.3 Columbia-Suicide Severity Rating Scale(C-SSRS), Suicidal Behavior by Type (Safety Sample)

- CT-13.1.4 Columbia-Suicide Severity Rating Scale(C-SSRS), Treatment Emergent Suicidal Ideation and Behavior (Safety Sample)
- CT-13.1.5 Columbia-Suicide Severity Rating Scale (C-SSRS) Listing of Treatment Emergent Suicidal Ideation (Safety Sample)
- CT-13.1.6 Columbia-Suicide Severity Rating Scale (C-SSRS) Listing of Treatment Emergent Suicidal Behavior (Safety Sample)
- CT-13.1.7 Columbia-Suicide Severity Rating Scale (C-SSRS) Listing of Treatment Emergent Serious Suicidal Ideation (Safety Sample)
- CT-13.1.8 Columbia-Suicide Severity Rating Scale (C-SSRS) Listing of Worsening Suicidal Ideation (Safety Sample)

13 References

- Otsuka Pharmaceutical Development & Commercialization, Inc. A phase 3, multicenter, randomized, double-blind, placebo-controlled trial of brexpiprazole in treatment of children and adolescents with irritability associated with autism spectrum disorder. Protocol 331-201-00148, issued 26 Apr 2019, amended 14 Aug 2019, 22 Nov 2019, 12 Feb 2020, 06 Jul 2020, and 07 Jul 2022.
- Otsuka Pharmaceutical Development & Commercialization, Inc. A phase 3, multicenter, open-label trial to evaluate the long-term safety and tolerability of brexpiprazole (OPC-34712) in the treatment of children and adolescents with irritability associated with autism spectrum disorder. Protocol 331-201-00191, issued 02 May 2019, amended 09 Sep 2019, 06 Nov 2019, 12 Feb 2020, 06 Jul 2020, and 07 Jul 2022.
- Centers for Disease Control and Prevention. Division of Nutrition, Physical Activity, and Obesity. SAS Program for the 2022 CDC Growth Charts that Includes the Extended BMI calculation. Available from: https://www.cdc.gov/nccdphp/dnpao/growthcharts/resources/sas.htm. Updated Dec 15, 2022. Accessed Dec 19 2022

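### Treatment-emergent serious suicidal ideation is counted only from a baseline of no ideation, so a child moving from rating 1-3 to 4-5 is missing from the serious row and its listing

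*SAP*

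**What the plan says.** SAP 8.7 lists four categories of treatment-emergent suicidality, each summarized by visit and for the overall treatment period. Three concern ideation:

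- Category (1), emergence of ideation: "reporting of any types of suicidal ideation during the treatment period while there was no suicidal ideation at baseline".
- Category (2), emergence of serious ideation: "having observation of suicidal ideation severity rating of 4 or 5 during the treatment period while there was no suicidal ideation at baseline".
- Category (3), worsening of ideation: "having a suicidal ideation severity rating that is more severe compared to baseline".

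Category (4) concerns behavior.

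SAP 11.8 sets the scale: "Suicidal ideation has 5 types of ideations with increasing severity from Type 1 to Type 5". It also sets the value used: "The most severe type of ideation on the subject at the visit level will be used for data summary purpose". The opening of SAP Section 8 takes the safety baseline as the "last observation or assessment in the variable prior to the first dose of the open-label IMP".

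SAP Section 12 plans a table of treatment-emergent ideation and behavior (CT-13.1.4), a listing of treatment-emergent serious ideation (CT-13.1.7), a listing of worsening ideation (CT-13.1.8) and a table of ideation by type (CT-13.1.2). SAP 8.7 describes the by-type tabulation with no condition on baseline.

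**The concern.** Category (2) raises the on-treatment threshold to 4 or 5 but keeps the baseline condition of category (1), which is no ideation of any type. It is therefore a subset of category (1). Escalation to a rating of 4 or 5 from lower-grade ideation falls outside both and lands in category (3), which has no threshold.

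This differs from the SAP's handling of other safety data. In SAP 8.1 an adverse event already present at baseline counts as treatment-emergent if it intensifies or becomes serious. In SAP Table 8.4-1, new onset of QTc above 500 msec requires only that the same limit was not exceeded at baseline. The matching rule here would be no rating of 4 or 5 at baseline.

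Analysis of suicide events on the C-SSRS is one of the safety endpoints serving the primary objective (Protocol 3.5.1, SAP Section 8). A reader of the serious row, or of the listing with that title, would reasonably take it to hold every child who newly reached a rating of 4 or 5 on treatment. It would not.

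**Working it through.** The plan gives no figure to reproduce on this point, and the trial is descriptive (Protocol 7.4.1). The check is a count over the possible rating pairs, followed by a check that the pairs in question can occur.

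**Step 1. Set-up.** Let b be the baseline rating and w the worst on-treatment rating, each from 0 (no ideation) to 5. There are 6 × 6 = 36 pairs. The rules in SAP 8.7, read literally, are:

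- Category (1): w ≥ 1 and b = 0
- Category (2): w ≥ 4 and b = 0
- Category (3): w > b
- Newly reaching 4 or 5: w ≥ 4 and b ≤ 3

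**Step 2. Pairs that newly reach 4 or 5.**

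| Pairs (b, w) | Number | Category (1) | Category (2) | Category (3) |
|---|---|---|---|---|
| (0,4), (0,5) | 2 | yes | yes | yes |
| (1,4), (1,5), (2,4), (2,5), (3,4), (3,5) | 6 | no | no | yes |

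The current rule captures 2 of 8 pairs. These are counts of possible transitions, not of children, and the pairs are not equally likely.

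**Step 3. What worsening mixes together.** Of the 36 pairs, 6 have w = b, so (36 − 6)/2 = 15 have w > b. They are:

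- the 8 pairs above;
- 6 that stay below 4: (0,1), (0,2), (0,3), (1,2), (1,3), (2,3);
- 1 that was already serious: (4,5).

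8 + 6 + 1 = 15. The worsening row cannot separate the 8 from the rest.

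**Step 4. Whether the by-type table fills the gap.** CT-13.1.2 counts types 4 and 5 whatever the baseline. It includes the 6 pairs, and it also includes a child already at 4 or 5 at baseline. It gives the number observed at 4 or 5, not the number who newly reached it.

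**Step 5. Whether baseline 1-3 can occur.** For direct rollovers, Protocol Table 3.4.3-1 has five exclusions. None is a C-SSRS criterion; number 4 is a general judgement. For delayed rollovers, criterion 3 of COVID-19 Addendum Table 3.2-1 excludes on ideation Items 4 and 5, and on clinical judgement of significant risk. Items 1-3 do not by themselves exclude. So baseline 1-3 is possible on both routes.

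**Step 6. Size.** One child among N subjects is 100/N percentage points. SAP Section 4 caps N at the 119 randomized in the parent trial: 100/119 = 0.84. With fewer subjects, or within one prior-treatment column (SAP 10.5), one child weighs more. The documents give no baseline ideation rate, so the expected number of such children cannot be computed.

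**The case against.** The strongest reply is that the scheme is coherent and loses nobody. Categories (1) and (2) share one baseline condition, and category (3) takes any increase from any baseline. A child going from 2 to 4 is in the worsening count, is listed individually in CT-13.1.8, and is under type 4 in CT-13.1.2. With at most 119 subjects, a reader can pick the case out of the listing. No test or decision rule depends on the count, and the C-SSRS is given at every treatment visit, so clinical detection of a case does not rest on a table label. Whether emergence is measured from 0 or from 0-3 is a choice between two workable conventions.

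Most of this stands. A reader might infer that these children go unreported, or that the plan understates the suicidality signal as a whole. The documents support neither: the by-type table counts every child rated 4 or 5 on treatment. Nor do the documents show that children with low-grade ideation are at greater risk of escalation, and the point does not need that claim.

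Two things remain. The number of children newly reaching 4 or 5 appears in no summary row and must be rebuilt from listings. And the convention chosen is out of line with the SAP's own adverse-event and QTc rules.

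**Conclusion.** The point holds as a defect in one category and its listing. Read literally, SAP 8.7 leaves all six transitions from baseline 1-3 to 4-5 out of the emergent serious row of CT-13.1.4 and out of CT-13.1.7. They are reported as worsening and by type, but no summary row isolates them.

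The effect on subject counts is unknown and may be nil. Each affected child would change the overall row by about 0.8 percentage points at 119 subjects, and by more with fewer. The conclusion assumes that the definitions are programmed as written and that some children enter with ideation rated 1-3, which the entry criteria permit but the documents do not quantify. It does not threaten the trial's conclusions. It is worth correcting before database lock because it concerns a primary safety endpoint and the correction is small.

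**What to change.** In SAP 8.7, define category (2) as an ideation rating of 4 or 5 during the treatment period with no rating of 4 or 5 at baseline, that is, baseline 0-3. Keep the current count, from no ideation at baseline, as a sub-row. Apply the same rule to CT-13.1.4 and CT-13.1.7. A table of baseline rating against worst on-treatment rating would also make the transitions visible and could be added.

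The cost is one SAP sentence and a small programming change, with no new data and no inferential result affected. Because the 2 pairs now counted are contained in the 8, the serious count can only stay the same or rise. A possible slight rise is the only downside.

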8.8 Concomitant Medications

Concomitant medications will be coded using the latest version of the World Health Organization (WHO) drug dictionary. The number and percentage of subjects taking concomitant medications prior to the open-label treatment period, during the open-label treatment period, and during the follow-up period will be respectively tabulated by drug classification, based on the Safety Sample.

8.9 Extent of Exposure

An individual subject's Total Days of Exposure to IMP is calculated as: last dose date – first dose date + 1, regardless of any gaps in treatment (such as dose interruption or omission) during the 26-week open-label treatment period. The variable Total Days of Exposure will be summarized on the Safety Sample by using descriptive statistics for a continuous variable.

The number and percentage of subjects who received the IMP during the open-label treatment will be calculated by dosing week. The dosing week will be based on the actual week since the start of the open-label dosing (ie, Days 1 to 7 as Week 1, Days 8 to 14 as

Week 2, etc). An individual subject's Average Daily Dosage will be derived for each dosing week by dividing the subject's total doses taken during the week by the number of his/her exposure days in that week. Note that the number of exposure days in a dosing week is not always equal to 7. It can be less than 7 for the week in which early treatment discontinuation occurs. Note that the number of exposure days in a week will not be adjusted for any gaps in treatment during the week. The variable Average Daily Dosage will be summarized by dosing week by using descriptive statistics.

9 Efficacy Analysis

All efficacy analysis will be performed on the Efficacy Sample.

9.1 The Secondary Endpoints

The secondary endpoints for this trial pertain to a few efficacy variables constructed from the rating scales (see Section 11). Two key efficacy variables are the ABC-I subscale score and the CGI-S score. Each of these variables and the change from baseline in each of them will be summarized on the OC data by visit and additionally on the LOCF data for the last visit at Week 26, by using descriptive statistics for continuous variables.

Confidential - Proprietary Information

9.3 Interim Analysis

No interim analysis is planned.

9.4 Multiplicity Adjustment

Not applicable.

10 Conventions

10.1 Software for Statistical Analysis and Reporting

The Statistical Analysis System® (SAS®, version 9.3 or newer) will be used for all statistical analysis and reporting.

10.2 Study Day

The open-label IMP dosing will start on the very next day after the last assessment visit of the double-blind period of the parent trial (Trial 331-201-00148).

For this trial, study day is derived as follows: (1) study day = observation date – IMP dosing start date + 1, for observation date \geq IMP dosing start date; (2) study day = observation date – IMP dosing start date, for observation date < IMP dosing start date. The open-label IMP dosing start date is referred to as Day 1.

10.3 Visit Window and the Derived Analysis Visit

The analysis visit variable will be needed for the by-visit analysis (including summary). For efficacy parameters and selected safety parameters (including all ABC subscales, CGI-S, \square SAS, AIMS and BARS), the analysis visit will be derived per Table 10.3-1 below. Observations or assessments at the ET visit or any other unscheduled visit will be programmatically mapped to an analysis visit per Table 10.3-1 below. If an observation date is \le (the last dose date + 7), then the mapping algorithm in Table 10.3-1

below applies; else if an observation date > (the last dose date + 7), then the observation will be excluded from data analysis.

For all other parameters, the protocol-specified scheduled visit per se (as recorded on the eCRF) will be taken as the analysis visit.

| Table 10.3-1 Mapping of the Analysis Visit for the Open-label Treatment Period | | |
|--|--|--|
| Analysis Visit | Target Study Day ^a per Protocol | Study Day ^a Interval (end points inclusive) |
| Day 1 | 1 | 1 |
| Week 1 | 7 | 2 to 10 |
| Week 2 | 14 | 11 to 17 |
| Week 3 | 21 | 18 to 24 |
| Week 4 | 28 | 25 to 42 |
| Week 8 | 56 | 43 to 77 |
| Week 14 | 98 | 78 to 112 |
| Week 18 | 126 | 113 to 140 |
| Week 22 | 154 | 141 to 168 |
| Week 26 | 182 | 169 to 196 |

^a See Study Day definition in Section 10.2.

The preceding algorithm ensures that all observations collected at the ET visit or any other unscheduled visit will be mapped to an analysis visit. In the instances where multiple observations (of same parameter on the same subject) fall into one study day interval, all values of the multiple observations in the study interval will be included for listings, but only the last observation (in the study day interval) will be used for the byvisit analysis.

10.4 Descriptive Statistics for Continuous and Categorical Variables

For continuous variables, descriptive statistics include N (which is number of subjects with non-missing value), mean, standard deviation, median, quartile, minimum and maximum. For categorical (eg, nominal or dichotomous) variables, descriptive statistics refer to frequency distribution (eg, count and percentage). Unless stated otherwise, ordinal variables such as assessment scores on all the scales used for this trial will be treated as continuous. Wherever possible, inferential statistics will be accompanied by descriptive statistics for presentation. Descriptive statistics can be used alone for data summary purpose, for example, for summarizing baseline demographic characteristics, medical history, etc. Unless specified otherwise, the denominator used for calculating percentage will be the number of unique subjects in the analysis sample (or its subgroups). And whenever applicable, a row of "Missing/Unknown" will be presented along with rows of recorded outcomes for the tabulation of the categorical variables.

10.5 Display of Statistical Outputs

Unless stated otherwise, data analysis and summary will be performed for the overall analysis sample (or the subgroups of interest) and separately for the two prior treatment groups. Thus, a statistical table output generated via SAS® programming will display the following three columns: (1) prior brexpiprazole; (2) prior placebo; and (3) all.

Wherever applicable statistical listings should be sorted by prior treatment group, subject ID, date of assessment, visit, etc. And in general, the listing should present the sorting variables, prior treatment, baseline demographics and all the variables of interest.

11 Scales: Rules for Scoring and Handling of Missing Data

11.1 ABC Subscales

The ABC scale has 58 items, which divide into 5 subscales as follows: (1) Irritability, Agitation; (2) Lethargy, Social Withdrawal; (3) Stereotypic Behavior; (4) Hyperactivity, Noncompliance; and (5) Inappropriate Speech. Each of the 58 ABC items is rated on a 4-point scale (0 = not at all a problem; 1 = the behavior is a problem, but slight in degree; 2 = the problem is moderately serious; 3 = the problem is severe in degree).

[figure not shown]
The Irritability subscale (ABC-I) subscale score is the sum of the ratings over 15 ABC items as follows. Item 2: injuries self on purpose; Item 4: verbally or physically aggressive to other children or adults; Item 8: scream inappropriately; Item 10: temper tantrums or outbursts; Item 14: irritable and whiny; Item 19: yells at inappropriate times; Item 25: depressed mood; Item 29: demands must be met immediately; Item 34: cries over minor annoyances and hurts; Item 36: mood changes quickly; Item 41: cries and screams inappropriately; Item 47: stamps feet or bangs objects or slam doors; Item 50: deliberately hurts himself/herself; Item 52: does physical violence to self; Item 57: has temper outbursts or tantrums when he/she does not get own way. Thus, ABC-I subscale score ranges from 0 to 45. For a visit, a subject's ABC-I subscale score will be unevaluable and set to missing if less than 12 of the 15 items are recorded for the visit. If 12, 13 or 14 of the 15 items are recorded, the ABC-I subscale score will be the mean of the recorded items multiplied by 15 and then rounded to the first decimal place. To state equivalently, if more than 20% of the component items have missing ratings (or say, not recorded), the ABC-I subscale score will be set to missing; otherwise, the total score will be the mean of the recorded items multiplied by 15.

The ABC subscale score on Social Withdrawal, Stereotypic Behavior, Hyperactivity/Noncompliance, and Inappropriate Speech is respectively the sum of

[figure not shown]
ratings over 16, 7, 16 and 4 individual ABC items. For each of these 4 subscales, if more than 20% of the component items have missing ratings (of note, at the subject-visit level), the subscale score will be set to missing; otherwise, the subscale score will be the mean of the recorded items multiplied by the total number of component items for the subscale.

